4.3 Exploratory Endpoints

- Memory and attention using Repeatable Battery for the Assessment of Neuropsychological Status (RBANS)
- Executive function using Trail Making Parts A and B

5 Study Design

This study is a single center trial designed to assess the safety of administering intranasal (IN) regular insulin in subjects with type 1 diabetes and intact hypoglycemia awareness Figure 4.

After written informed consent has been obtained, subjects will be screened to assess study eligibility based on study inclusion/exclusion criteria. Subjects who are eligible at the end of the screening visit (Visit 1) will be scheduled for a baseline visit to take place 1 to 2 weeks later (Visit 2). During the baseline/randomization visit, subjects will be administered the hypoglycemia and cognitive questionnaires and tests. Patients then are randomized 1:1 to either treatment with intranasal insulin or placebo. They will wear two 10-day real-time CGMs, and then crossover to the other group for another two 10-day period following a 2 week washout period. A final safety/assessment visit will take place up to 1 week after visit 10.

5.1 Drug Administration Training

All subjects will receive training at start of treatment visits regarding home administration of IN insulin using the SipNose device during visits 2 and 7. Subjects will be required to administer the dose twice daily, one in the morning and the other in the evening (at least 8 hours between doses). If the SipNose device is discharged prior to insertion into the nose, then a retrial admission would be indicated. However, if the device is discharged following nasal insertion, then a retrial would not be permitted. The steps to ensure that subjects maintain compliance with the study protocol over 4 weeks include conducting the following:

- In-clinic training sessions: baseline/randomization (Visit 2) and start of treatment period 2 (visit 7)
- Phone call from study coordinator/investigator 1 day and 5 days after baseline visit and after Visit 7.

[figure not shown]

Figure 4: Study Design Flow Diagram

5.2 Drug Administration with SipNose

Each dosing administration will require the following items: a) 2 SipNose Devices (2) 2 nose piece covers; b) device holder; c) study drug vial (10 ml vial of regular Insulin (Humulin-R or Placebo)); d) Insulin syringe; e) alcohol wipe; f) needle clipper and/or sharps container.

[figure not shown]

Figure 5: SipNose Device -Sp1N1C1

During the baseline/randomization visit the subject will administer the study drug in front of study personnel to ensure adherence to study protocol for drug administration. To ensure safety and medication compliance, subjects will be followed-up with a routine phone call 1 day and 5 days after baseline/randomization visit, 1 day and 5 days after Visit 7 (start of treatment period 2) and 1 week after final treatment visit.

Devices will be shipped to the clinical study site. One device with a nose piece cover will be supplied for each dose to be administered in the study. Devices are one-time use only. A kit containing all necessary items will be distributed to each subject and replaced at each study visit or as necessary. This will include several extra devices in case there are issues with any devices. Each device is to be loaded with a 10 unit dose of study drug to be used immediately or up to a maximum of 10 minutes prior to IN administration. The Nose Piece and Secondary Drug Container (temporary) are the only components of the device that will come into contact with the study drug and subject's nasal cavity.

5.3 Device Dose Loading and Administration

1. Gather and prepare the needed materials.

*Not the actual syringe and study drug. The above pic for illustration only.

Figure 6: Study Drug Administration Materials

2. Open the devices covers and place the devices in the device holder

Figure 7: Open Device Cover

3. Remove the protective cap from the study drug vial as shown in figure 8 if you have not already done this step.
4. Load the drug formulation into the device.
 - a. Remove the cap from the top of the vial.

- b. Wipe the top of the vial with an alcohol wipe.

[figure not shown]

Figure 8: Remove Cap (A) and Cleaning Vial (B)

- c. Immediately before (within 10 minutes) of taking dose, load the 0.1 ml (10 Units) desired study drug dose volume from the vial using the Insulin syringe following the instructions provided with the drug formulation.
- Pull syringe plunger down to 0.1 ml (10 Units)
 - Push air into the vial
 - Turn the medication vial upside-down and slowly pull the syringe plunger down, withdrawing the study drug until 0.3ml (30 Units) line is visible just above the plunger. Tap the syringe to move any air bubbles to the top

[figure not shown]

Figure 9: Filling Syringe

- Slowly push the plunger up to the 0.1ml (10 Units) line to push any air bubbles back into the vial.
 - Turn the medication vial upright and gently pull the syringe without moving the plunger.
- d. Insert the syringe with the needle carefully into the top of the device (Figure 10).
- e. Slowly depress the syringe plunger, ensuring that no study drug leaks from the device. After the plunger is fully depressed, remove the syringe with the needle carefully from the device and leave the device in the device holder.
- f. Dispose of the syringe with the needle by using a needle clipper and/or a sharps container.
- g. Repeat these steps, using another syringe for the second device.
- h. The study drug must be administered within 10 minutes after loading it into the device.
5. Instruct the subject to blow their nose into tissue prior to administering the first dose.

Figure 11: Filling SipNose Device

6. Instruct the subject to turn the device upside down and flick the nose piece to allow the drug to concentrate at its edge as shown in the figure below (Figure 10). This helps the subject to see if the drug is loaded prior to administration.

[figure not shown]

Figure 10: Prepare Device for Administration

7. The research staff will provide guidance to the subject on placement for nasal administration for the first dose.
 - a. Place the nose piece of the device comfortably in the nose as shown in the figure below (Figure 12)
 - b. After the initial placement, the examiner will make slight adjustments to orient the nose piece in the proper direction (parallel to the nasal septum).

[figure not shown]

Figure 12: Placement of Device for Nasal Administration

8. Use thumb to press the activation button to administer the drug in the nasal cavity.

9. Without blowing nose, repeat steps 6-8 for the other nostril using the second prepared device.
10. Place used devices into the Ziploc bag in the dosing kit to be returned to the study staff for disposal via biohazard waste. Devices that malfunction will be placed into a separate plastic bag and returned to SipNose for quality inspection.

5.4 CGM Device and Training

CGM device and smartphone app training will occur at the start of both treatment periods, and user guide materials will be provided. Participants will first download the Dexcom G6 Mobile app to their smartphone. After entering their transmitter's serial number into the app, there is a 2 hour warm-up for the CGM. Next they will identify a location on their abdomen as directed by study staff for insertion of the sensor. After cleaning the skin, participants are instructed how to use the applicator to insert the sensor and connect the transmitter to the sensor. After the 2 hour warm up is over, the CGM will start transmitting real-time glucose data. Participants will be allowed to use CGM data for their diabetes management. Blood glucose monitoring can be performed using the participant's own glucose meters if CGM readings do not match a participant's symptoms. CGM alert thresholds will be set at default levels of 70 mg/dL for low glucose, and 180 mg/dL for high glucose. These alerts can be adjusted during the study as needed. The G6 app also has a feature where wearers can mark events such as food or exercise; for the purposes of this study, participants will be instructed to use the "other" activity as a marker of symptomatic hypoglycemia (which they can use as an alternative to the hard-copy participant journal for documentation of symptomatic hypoglycemia)

[figure not shown]

Figure 13: Inserting the CGM Sensor

The Dexcom G6 system allows for the wearer to share their glucose data with up to 5 followers remotely through the Follow app. This "sharing" feature will be downloaded and started with assistance of the study staff. The study staff, including the PI, will have 24 hour access to this data for safety purposes, if participants call with any concerns during the study. A CLARITY mobile account will be set up for participants (using the CLARITY app which links to the G6 Mobile app) and linked to the research site, which can capture device data for analysis.

5.5 Outcome Measures

CGM data will be downloaded at the end of each treatment period. We will capture percent time in each glucose range of interest as well as mean glucose and other glycemic metrics. Hypoglycemia unawareness questionnaires, cognitive tests, and neuropathy tests will be collected at beginning and end of the first treatment period and at the end of the second treatment period. AE's will be assessed throughout the study. The remaining safety outcomes will only be measured at screening and post-study completion.

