7.1.1 Visit 1: Screening (Day -14 to -7)

The following procedures will be performed at this visit:

- Obtain written informed consent from subject prior to any study related procedures
- Obtain Gold score – if <4, can stop here.
- Review inclusion/exclusion criteria
- Review medical history, as it pertains to inclusion/exclusion criteria
- Obtain subject's demographic information (date of birth, gender, race, education, etc.)
- Obtain details of medications, prescription, over the counter and vitamin/nutraceuticals taken over the course of the last 30 days prior to screening
- Collect vital signs (blood pressure & pulse), height, weight and BMI
- Obtain laboratory studies (Na, K, CO₂, Creat/GFR, AST/ALT, CBC w/ diff) and HbA1c POC, if not obtained within the past 3 months
- Urine pregnancy test in women of child bearing potential
- Perform a standard 12-lead ECG
- Download participant's blood glucose meter and/or CGM to evaluate recent glucose control
- Provide patients with glucagon self-injection kit, if they do not have a current kit at home
- Provider to see patient at this visit for visit assessment review

7.1.2 Visit 2: Randomization/Start of Treatment Period 1 (Day 0) - This will be scheduled as a morning appointment to accommodate visit length

The following procedures will be performed at this visit before SipNose administration:

- Assess for AE/SAEs
- Collect vital signs (blood pressure & pulse)
- CGM placed and started before testing (requires 2 hour warm up)
- Document BG values before and after cognitive testing
- C-SSRS questionnaire
- MNSI survey
- Hypo surveys (Clarke, HypoAQ)
- Cognitive tests (RBANS, Trail-making)
- Smell test (12-item UPSIT test versions A & B)
- Ensure patient still meets inclusion/exclusion criteria
- Randomize after completion of cognitive testing and hypo surveys
- SipNose device teaching

Administer first dose of intranasal insulin in clinic after above testing done, observe patient for 4 hours (only if randomized to intranasal insulin for treatment period 1).

The following procedures will be performed after the first dose is administered:

- Teach daily diary (or how to document within the Dexcom G6 app that symptomatic hypoglycemia is commencing)
- Teach glucagon and hypoglycemia management
- Teach CGM & apps (Including G6, Clarity, Follow apps); provide user guide materials
- Download participant's SMBG (if used) and/or CGM, and review for hypoglycemia and overall glucose control

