7.1.5 Visit 5: End of Treatment Period 1 (Day 17 +/- 3 days)

The following procedures will be performed at this visit:

- Safety check and assess AEs/SAEs
- Gold score (for data collection purposes only)
- Medication review for any changes since screening
- VS (blood pressure/pulse)
- MNSI survey
- Hypo surveys
- Document BG values before and after cognitive testing
- Cognitive tests (study drug must have been taken prior to testing)
- Review daily diary
- Evaluate CGM for adequate data collected
- Inventory returned devices
- Download SMBG for safety, if used
- Download and review CGM data
- Provider to see patient at this visit for visit assessment review
- In the event the study site is recommending no non-essential in person clinic contacts (such as during the COVID-19 pandemic), this visit may be done remotely and study staff will obtain as much of the above procedural information as possible. Procedures such as MNSI survey and VS may not be able to be done.

7.1.6 Phone Visit 6: Safety Check 1 Week into the 2 Week Washout (Day 24 +/-2 days)

The following procedures will be performed at this visit:

- Study staff phone call to assess for AEs/SEs

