7.1.7 Visit 7: Crossover/Start of Period Treatment 2 (Day 31 +/- 2 days)

The following procedures will be performed at this visit:

- Safety check and assess AEs/SAEs
- Medication review for any changes since screening

- Vital signs (blood pressure/pulse)

Administer first dose of intranasal insulin in clinic after above testing done, observe patient for 4 hours (only if randomized to intranasal insulin for treatment period 2).

The following procedures will be performed after the first dose is administered:

- SipNose device teaching
- Teach daily diary (or how to document within the G6 app that symptomatic hypoglycemia is commencing)
- Teach glucagon and hypoglycemia management
- Download SMBG for safety (if used)
- CGM placed
- Teach CGM & apps (Including G6, Clarity, Follow apps); provide user guide materials
- Provider to see patient at this visit for visit assessment review
- Subject instructed to call if any hypoglycemia before phone call occurs the next day
- In the event the study site is recommending no non-essential in person clinic contacts (such as during the COVID-19 pandemic), this visit may be done remotely and study staff will obtain as much of the above procedural information as possible, IF the participant is beginning the saline phase of the study only (not for insulin start). Distribution of supplies may be done remotely as well. If the participant is to begin the intranasal insulin part of the study, then the washout will be extended until a time when non-essential clinic visits at the site are permitted.

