12.3 Statistical Analysis of Secondary and Exploratory Outcomes

The secondary and exploratory objectives are purely descriptive. No inferential statistics will be performed. All measures of overall glycemic control, hypoglycemia awareness, and safety endpoints will be reported using the appropriate summary statistics. Values will be reported from baseline and conclusion of each dosing period.

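### Awareness questionnaires and the MNSI are not taken at the start of Period 2, so change within that period and return to baseline after washout cannot be described

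*Combined protocol and SAP*

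**What the plan says.** Objectives 2 and 3 in section 3.2 are to describe how awareness and safety measures change under intranasal insulin. Section 4.2 measures awareness in three ways: three questionnaires (Gold, Clarke, HypoA-Q) and two measures built from CGM and participant journals. It lists change in neuropathy tests as a safety outcome.

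Section 5.5 sets the timing. Questionnaires, cognitive tests and neuropathy tests are "collected at beginning and end of the first treatment period and at the end of the second treatment period". The visit lists in section 7.1 largely agree:

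- Visit 1 (Day -14 to -7): Gold only.
- Visit 2 (Day 0): MNSI, Clarke, HypoA-Q and cognitive tests. Gold is not listed, although 5.5 places the questionnaires here.
- Visit 5 (Day 17 ± 3): Gold, MNSI, hypoglycemia surveys and cognitive tests.
- Visit 6 (washout call): adverse events only.
- Visit 7 (Day 31 ± 2), before dosing: an adverse event check, "Medication review for any changes since screening", and vital signs.
- Visit 10 (Day 48 ± 3): Gold, MNSI, Clarke, HypoA-Q and cognitive tests.

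Section 12.3 makes the secondary and exploratory outcomes descriptive, without inference, and adds: "Values will be reported from baseline and conclusion of each dosing period".

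**The concern.** The sentence in 12.3 can be read in two ways. If each dosing period has its own baseline, the plan promises a Period 2 value that no visit collects. If there is a single baseline, Day 0 is the natural candidate, because section 5 calls Visit 2 the baseline visit. Change with insulin then means different things in the two sequences. For insulin-first participants it covers the insulin period alone. For insulin-second participants it covers placebo, washout and insulin together.

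The second difficulty is carry-over. The crossover relies on awareness returning to its starting level within two weeks, and nothing measured between Visit 5 and dosing at Visit 7 shows whether it does. The protocol gives reasons not to take this for granted. Its background links repeated hypoglycemia to loss of awareness and suggests that intranasal insulin may help counter-regulation. Section 5.4 lets participants act on real-time CGM throughout.

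**Working it through.** **The plan's own figure.** Section 12.4 gives 79.8% power for the primary endpoint with N = 10, within-subject SD 1.4% and margin 2%. SE = 1.4 × √(2/10) = 0.626; noncentrality = 2/0.626 = 3.194; critical t on 8 df at one-sided 0.025 = 2.306. Power is 79.84%, so the figure is reproduced. Nothing below depends on it or changes it.

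**Spans from Day 0 to the end of insulin** (visit days from section 7.1; Day 0 as baseline is an assumption):

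- Insulin-first: 17 - 0 = 17 days, window 14-20.
- Insulin-second: 48 - 0 = 48 days, window 45-51.
- Ratio: 48/17 = 2.8. Time not on insulin in the longer span: 48 - 17 = 31 days, and 31/48 = 65%.
- Gold, from screening: 17 + 7 to 17 + 14 = 24-31 days, against 48 + 7 to 48 + 14 = 55-62 days. These differ by the same 31 days.
- Visit 5 as the Period 2 reference: 48 - 17 = 31 days (25-37), starting from an on-placebo value.

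Under clinic restrictions, 7.1.7 extends the washout only for participants about to start insulin, so only the longer span can grow.

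**What cancels.** Let τ be the insulin-minus-placebo effect at the end of a period, δ a shift between Day 17 and Day 48 common to everyone, and λ any insulin effect still present at the end of Period 2 in the insulin-first sequence. The within-subject difference, insulin minus placebo, is:

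- insulin-first: τ - δ - λ
- insulin-second: τ + δ

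The average of the two sequence means is τ - λ/2. Drift drops out, whatever its shape and whatever the split of completers. Half the carry-over remains. Subtracting a shared Day 0 value from both periods leaves this result unchanged.

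Raw change from Day 0 to the end of insulin, reported alone, keeps the drift. With 5 per sequence the mean span is (5 × 17 + 5 × 48)/10 = 32.5 days for each treatment. If 6 insulin-first and 4 insulin-second participants are simply pooled, it is (6 × 17 + 4 × 48)/10 = 29.4 days for insulin and (6 × 48 + 4 × 17)/10 = 35.6 days for placebo.

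**Can carry-over be seen indirectly?** The available check compares the sum of the two end-of-period values between sequences. Assume λ equals one within-subject SD (set to 1), 5 per sequence and two-sided 0.05. With intraclass correlation ρ, the between-subject variance is ρ/(1 - ρ), and SE = √[(4ρ/(1 - ρ) + 2) × 2/5].

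| Assumed ρ | SE | Power |
|---|---|---|
| 0.5 | 1.55 | 9% |
| 0.7 | 2.13 | 7% |
| 0.9 | 3.90 | 6% |

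Comparing Day 31 minus Day 0 between sequences has SE = √(2 × 2/5) = 0.894 and power of about 17%. That is still not a usable test, but each participant's return to baseline could be read directly.

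**With a Visit 7 measurement.** The insulin span becomes 17 - 0 = 17 days (14-20) in one sequence and 48 - 31 = 17 days (12-22, windows taken independently) in the other.

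**The case against.** The strongest reply is that a 1:1 crossover is built for this situation. Each treatment is observed at Day 17 in one sequence and at Day 48 in the other, so unequal spans do not bias the treatment comparison. A reader might infer from 17 against 48 days that drift is inseparably mixed with the insulin effect. The algebra above shows otherwise for a within-subject contrast. That part of the objection stands in full; what it leaves is that 12.3 does not specify such a contrast, and that carry-over survives it.

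It is also fair that 12.3 never defines change from Day 0 for Period 2, so the 17/48 figures are conditional. Reporting end-of-period values is close to what 12.3 already says. The objectives, however, are worded as changes, so the baseline has to be stated.

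A reader might also infer that the awareness objective cannot be met. The documents do not support that: the two CGM and journal measures are gathered during each period and need no Visit 7 questionnaire.

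Finally, the added data are modest. About 17% power is no carry-over test. The questionnaires' recall windows are in Appendix 4, which is not reproduced; if one exceeds the washout, a Visit 7 score would partly reflect Period 1. Both limits stand.

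**Conclusion.** The gap is real and limited in reach. As written, the plan cannot describe within-period change in Period 2 for Gold, Clarke, HypoA-Q or MNSI, and cannot show whether these return to baseline after washout. If Day 0 is the baseline, insulin change spans 17 days in one sequence and 48 in the other; for Gold it is 24-31 against 55-62 days. These are nominal figures and assume no washout extension.

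Nothing in the documents shows that carry-over occurs; the point is that it would not be directly observed. Only the questionnaire and MNSI parts of descriptive secondary outcomes are touched, together with the cognitive tests that share the schedule. The primary CGM endpoint, the CGM and journal awareness measures and the stated power are unaffected. The correction is worth making because it is cheap and lets the trial describe what its objectives name.

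**What to change.** - **7.1.7 and 5.5:** add Gold, Clarke, HypoA-Q and MNSI at Visit 7 before the first Period 2 dose, with the questionnaires by phone if the visit is remote. A remote Visit 7 is allowed only for participants starting saline, so MNSI may be missed in some insulin-first participants.
- **7.1.2:** add Gold at Visit 2, so that the list matches 5.5.
- **12.3:** report end-of-period values by treatment with the within-subject difference, averaged over the two sequence means. Add change from each period's own start, and Visit 7 minus Visit 2 as a descriptive check of return to baseline, stated not to be a carry-over test at N = 10.
- **Cognitive tests:** leave the schedule as it is. Section 7.6.2 provides three RBANS versions for three sessions, and a fourth session would repeat one.
- **If no forms are added:** describe Period 2 by end-of-period values only, and do not label them change with treatment.

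The cost is a few minutes of existing forms at a visit already scheduled, wording in four sections, and possible overlap of a Visit 7 score with Period 1 if a recall window is longer than the washout.

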5.6 Study Duration

Study participation will last approximately 10 weeks, consisting of a screening visit, 4 study phase visits, 1 follow-up safety assessment visit and at least 5 phone call visits. Subjects will receive treatment with IN insulin for a period of 14-20 days. Subjects who discontinue treatment will continue to complete follow-up measures as possible.

6 Study Population

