3.1 Primary Objective

Demonstrate no significant increase in dangerous hypoglycemia with administration of intranasal insulin in T1D participants with intact awareness of hypoglycemia.

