4.1 Primary Endpoints

Dangerous hypoglycemia defined by percent time below range (<54 mg/dL) from real-time continuous glucose monitoring (CGM).

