4.2 Secondary Endpoints

- Overall metrics and glycemic control from real-time CGM data during each treatment period defined as:
 - Percent time in range (70-180 mg/dL) from real-time CGM
 - Percent time below range (<70 mg/dL) from real-time CGM
 - Percent time above range (>180 mg/dL and >250 mg/dL) from real-time CGM
 - Mean glucose from real-time CGM
 - Coefficient of variation (%CV) from real-time CGM
 - Glucose management indicator (GMI) from real-time CGM
 - Percent time of active sensor wear from real-time CGM
- Hypoglycemia awareness measured three ways using:

- 3 hypoglycemia unawareness questionnaires/scores (Gold Score, Clarke survey, HypoA-Q)
- Time from CGM reading of, <70 mg/dL, 54-<70 mg/dL and <54 mg/dL to time of participant hypoglycemia awareness obtained from participant journals
- Glucose value from real-time CGM at onset time of hypoglycemia awareness obtained from participant journals
- Safety outcomes include:
 - Adverse events
 - Neuropathy test changes
 - Review of patient non-research insulin doses and medications
 - HbA1c
 - EKG
 - Smell test changes
 - C-SSRS assessment

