6.1 Eligibility Criteria

6.1.1 Inclusion Criteria

- Adult patients (age ≥ 18) with type 1 diabetes diagnosis and a duration of diabetes of at least 10 years
- Gold score < 4
- HbA1c $\geq 6.5\%$ within the last 3 months or at screen visit
- Stable insulin regimen (MDI or insulin pump) for at least 3 months, as deemed stable by principal investigator
- Depression/anxiety medications stable for at least 3 months
- Ability and willingness to wear CGM continuously during study participation
- Participants must use their own smartphone, and have the ability and willingness to use CGM smartphone applications compatible with their smartphone
- Ability and willingness to check SMBG using own supplies, as instructed by study staff
- Ability and willingness to document when having symptoms of hypoglycemia in the CGM smartphone app or in a diary
- If using insulin pump, willing to operate insulin pump without threshold suspend feature or hybrid closed-loop, if applicable
- Proficient in speaking, reading and understanding English in order to complete surveys and testing of cognitive function
- Women of child-bearing age must agree to procure and use contraception throughout the study

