12.1 Analysis Overview

Discrete variables will be summarized using frequencies and percentages, while continuous variables will be summarized by mean and standard deviation or median and interquartile range, as appropriate. Baseline variables will be compared between groups to ensure randomization achieved a balanced design. Distribution of the outcome variables will be assessed to determine if the planned analyses are appropriate. All analyses will be performed on an intention-to-treat basis. Missing data will be considered to be missing at random and those subjects will be excluded from analysis. If a large proportion of data is missing (>10%), we will compare baseline characteristics between subjects with missing and non-missing data. No adjustment for multiple comparisons will be done. All statistical analyses will be performed in SAS Version 9.4.

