12.2 Statistical Analysis of Primary Outcomes

The primary objective of this study is to assess non-inferiority of dangerous hypoglycemia with administration of intranasal insulin in T1D participants with intact awareness of hypoglycemia. A two-sided 95% confidence interval will be reported for the difference between the two treatment periods based on a least squares model. A non-inferiority margin

[figure not shown]

Figure 14: Possible outcomes of non-inferiority analysis

of 2% (approximately 30 minutes per day) will be used (see Section 12.4 for justification). The null hypothesis of inequality (difference is greater than or equal to 2%) is rejected in favor of the alternative hypothesis of equality (difference is less than margin) if the lower limit of the confidence interval is greater than -2%.

Since non-inferiority is typically framed in terms of a one-sided test, it is worth noting that the left half of a two-sided test at $\alpha = 0.05$ gives the same rejection region as a one-sided test at $\alpha = 0.025$. Therefore, reporting a two-sided 95% confidence interval will provide flexibility to test for inferiority if non-inferiority cannot be declared while maintaining the overall type 1 error rate at 5%. Figure 14 shows the inference to be drawn for various scenarios of the two-sided 95% confidence interval.

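### No on-treatment analysis accompanies the intention-to-treat non-inferiority test, so CGM days after a participant stops insulin could count as insulin exposure and favour a finding of safety

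*Combined protocol and SAP*

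**What the plan says.** The primary objective (3.1) is framed around taking the drug: "Demonstrate no significant increase in dangerous hypoglycemia with administration of intranasal insulin". The endpoint in 4.1 is CGM percent time below 54 mg/dL, with no data window given. Section 12.2 defines the contrast: "A two-sided 95% confidence interval will be reported for the difference between the two treatment periods based on a least squares model".

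Four provisions decide whose data enter that contrast, and from which days:

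- Section 5.6, on stopping study drug: "Subjects who discontinue treatment will continue to complete follow-up measures as possible".
- Section 12.1, on the analysis set: "All analyses will be performed on an intention-to-treat basis".
- Section 12.1, on gaps: "Missing data will be considered to be missing at random and those subjects will be excluded from analysis".
- Section 10.1, on completion: it is defined by attending the 11 visits, not by dosing. Someone who stops the drug but attends every visit is a completer.

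On sensor wear, eligibility (6.1.1) asks for "Ability and willingness to wear CGM continuously during study participation", which is tied to participation and not to dosing. Section 5.5 has CGM data downloaded at the end of each treatment period. No section restricts CGM data to days on drug, sets an adherence threshold, or plans a per-protocol or on-treatment analysis.

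**The concern.** In a superiority trial, dilution from stopped treatment works against the claim. In a non-inferiority safety trial it works for the claim. If insulin raises time below 54 mg/dL only while it is being taken, off-drug days averaged into the insulin period shrink the insulin-minus-placebo difference and make the margin easier to meet.

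Stopping may also be related to the outcome, because lows are a plausible reason to stop. The participants with the largest on-drug effect could then have the shortest exposure.

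This is separate from the missing-data rule in 12.1. Here the data are present but were collected off drug. With 10 participants, each one is a tenth of the evidence for the trial's only inferential claim.

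**Working it through.** **Inputs from the documents.** Margin 2% and two-sided 95% interval (12.2); N = 10, within-subject root mean square error 1.4%, true difference 0, power 79.8% (12.4); period length 17 days (Visit 5 at Day 17; Visit 10 at Day 48 minus Visit 7 at Day 31).

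**Assumptions.** The documents give no discontinuation rate. The scenarios take 1, 2 or 3 of 10 participants stopping insulin after Day 4, with CGM continuing to the end of the period and a complete placebo period. The on-drug increase is exactly 2%, the effect is nil once the drug stops, errors are normal and there is no period effect. Section 12.2 does not define the direction of the difference. Here it is insulin minus placebo, so non-inferiority means an upper limit below 2%.

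**Step 1: reproduce the stated power.** SE = 1.4 × √(2/10) = 0.626; df = 10 − 2 = 8; critical t = 2.306; noncentrality = 2/0.626 = 3.19. The noncentral t gives 79.84%, matching the stated 79.8%.

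**Step 2: error rate with full exposure.** With a true difference of 2%, the same test declares non-inferiority 2.5% of the time, as designed.

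**Step 3: dilution.** A stopper's expected difference is 2 × 4/17 = 0.47%. With s stoppers the expected mean difference is 2 × [(10 − s) + s × 4/17]/10, which is 1.85%, 1.69% and 1.54% for s = 1, 2 and 3.

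**Step 4: false non-inferiority.** A shortcut puts the shifted mean into the Step 1 formula and leaves the SE unchanged. That overstates the problem: when some participants have an expected difference of 0.47% and the rest 2%, the between-participant spread rises and the interval widens. A subject-level simulation of the 2×2 crossover includes that spread.

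| Stoppers (of 10) | Expected difference | Shortcut | Simulation |
|---|---|---|---|
| 0 | 2.00% | 2.5% | 2.5% |
| 1 | 1.85% | 4.1% | 3.7% |
| 2 | 1.69% | 6.3% | 5.4% |
| 3 | 1.54% | 9.5% | 7.7% |

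The simulated figures are the ones to use. Stoppers split as evenly as possible between the two sequences give 5.2% and 7.6% for 2 and 3. Later stopping matters less: with drug stopped halfway through the period, the rates are 3.3%, 4.3% and 5.6% for 1, 2 and 3 stoppers.

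**Step 5: precision of an on-treatment analysis.** If noise scales with the number of CGM days, a stopper's insulin-period SD becomes 1.4 × √(17/4) = 2.89%. Simulated power at a true difference of 0 falls from 79.8% to about 74%, 69% and 64% with 1, 2 and 3 such stoppers. Leaving stoppers out entirely gives 73.4% with 9 participants, and 66.5% (4+4) or 63.8% (5+3) with 8.

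**The case against.** A reader might infer that the plan states that off-drug CGM is scored as insulin. It does not. Section 5.6 promises only that follow-up continues where possible, and the sensor wording in 6.1.1 is an eligibility criterion about willingness. The phrase "Overall metrics and glycemic control from real-time CGM data during each treatment period" belongs to the secondary endpoints in 4.2. Continued wear is the natural reading, but it is an inference.

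Other routes also shrink the affected group. Section 10.3 lets the investigator end participation for adverse events or intolerance. A participant without usable data in both periods is excluded under 12.1. Neither route dilutes the difference, although both remove people who may have had lows. Severe hypoglycemia is captured as a serious adverse event (11.2, 11.6.1) and the DSMB reviews safety data (13.2), so serious harm would not go unseen.

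An on-treatment analysis has its own bias. It cuts the record at a time that may be related to the outcome, and sets a few days on insulin against a full placebo period.

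All of this stands, and it limits the size of the point and the form of the fix. It does not remove the gap. Termination under 10.3 is discretionary, 5.6 provides separately for people who stop the drug and stay, and the exclusion rule does not reach a stopper with complete CGM data.

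**Conclusion.** The concern holds in limited form. Sections 5.6, 12.1 and 12.2 together retain stoppers, analyse by assignment and contrast whole periods, with nothing alongside that addresses time on drug. For a non-inferiority claim about giving insulin, that combination leans towards declaring safety. In the scenarios above, one early stopper raises the error from 2.5% to about 3.7%; two roughly double it, to 5.4%; three roughly triple it, to 7.7%. These figures rest on assumed numbers and timing of stopping, and on stoppers continuing to wear the sensor.

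Two stronger conclusions are tempting and not supported. One is that the intention-to-treat result cannot support the objective if anyone stops early: a single stopper moves the error only modestly. The other is that non-inferiority should require both analyses to pass: with 10 participants that can only lower power below the planned 79.8%, and nothing in the documents calls for it. Continued follow-up and intention-to-treat are sound. The flaw is the missing companion analysis.

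**What to change.** Keep intention-to-treat as the primary analysis and make these additions:

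1. **Sections 12.1 and 12.2.** Pre-specify a supportive on-treatment analysis of percent time below 54 mg/dL, using the same model and CGM data from first to last study dose in each period. Set a minimum-data rule before the CGM data are analysed, and report how many participants fall below it.
2. **Section 5.6 or 12.2.** State whether participants who stop study drug keep wearing the sensor, and where the CGM window for the primary analysis ends.
3. **Visits 5 and 10.** Add a last-dose date field, completed from participant report, the compliance calls and the device inventory. The diary is described only as a record of symptomatic hypoglycemia. The compliance calls fall early in each period, and device counts do not date doses, so none of these supplies the date alone.
4. **Reporting.** Give both intervals. If they disagree about the margin, qualify the non-inferiority conclusion as not shown for time on drug.

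The cost is a paragraph of analysis text, one data field and a second run of the same model. The statistical downside is the wider on-treatment interval from Step 5 and the informative end of early stoppers' windows, which is why this analysis should be supportive and not a second hurdle. If nobody stops, the two analyses essentially coincide.
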